4.1.2. Exclusion criteria

Patients meeting any of the following criteria will not be included in the study:

- 1. Having a diagnosis of valvular atrial fibrillation, post-operative atrial fibrillation, rheumatic atrial fibrillation or mechanical-valvular atrial fibrillation during the baseline and post-index period
- 2. Having a cardiac surgery procedure record during the baseline period
- 3. Having a joint replacement procedure record during the baseline period
- 4. Having a procedure of prosthetic heart valve during the baseline period
- 5. Having a diagnosis of venous thromboembolism during the baseline period
- 6. Female patients with pregnancy during the follow-up period
- 7. Patients prescribed "off-label" doses of OACs (per Japanese package insert of each OAC) or patients treated with OAC but in "off-label" or "contraindicated" manners.

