5.4. COVARIATES

Items	definitions	roles
Gender	Male or female	Patient characteristics
		CCI
Body weight	≥ 60 kg or < 60 kg	Patient characteristics
eGFR (continuous)	Value in the baseline If a patient has multiple eGFR values, the values closest to the index date will be adopted	Patient characteristics
eGFR (categorical)	≥ 50 ml/min or < 50 ml/min	Patient characteristics
Serum creatinine (continuous)	Value in the baseline If a patient has multiple eGFR values, the values closest to the index date will be adopted	Patient characteristics

PFIZER CONFIDENTIAL

Serum creatinine (categorical)	≥ 1.5mg/mL or < 1.5	Patient
	mg/mL	characteristics
CHADS2	CHADS2 score will be calculated based on age and the presence of congestive heart failure, hypertension, diabetes, and stroke or TIA.	Patient characteristics
CHA2DS2-VASc	CHA2DS2-VASc score will be calculated based on age and the presence of congestive heart failure, hypertension, diabetes, stroke or TIA, vascular disease and sex category.	Patient characteristics
CCI		

Page 13 of 51

	CCI	
Medications		
CCI		
Treated with antiplatelet drug in baseline	Defined using prespecified drug- specific codes: Yes or No	Patient characteristics
PFIZER CO	NFIDENTIAL	

Page 14 of 51

		I
Treated with NSAIDs in baseline	Defined using prespecified drug- specific codes: Yes or No	Patient characteristics
Treated with gastric secretion inhibitor in baseline	Defined using prespecified drug- specific codes: Yes or No	Patient characteristics
Treated with statin-based drug in baseline	Defined using prespecified drug- specific codes: Yes or No	Patient characteristics
Treated with anti-hypertensives in baseline	Defined using prespecified drug- specific codes: Yes or No	Patient characteristics
Treated with anti-arrhythmics in baseline	Defined using prespecified drug- specific codes: Yes or No	Patient characteristics
Treated with beta-blockers in baseline	Defined using prespecified drug- specific codes: Yes or No	Patient characteristics
Procedures		
Cardioversion	Defined using prespecified medical procedure codes: Yes or No	Patient characteristics
Cardiac ablation	Defined using prespecified medical procedure codes: Yes or No	Patient characteristics
Anticogulation		
INR (warfarin cohort)	Continuous variable. * Only available for patients treated with warfarin	Patient characteristics
Apixaban doses	2.5 mg BID or 5mg BID * Only available for patients treated with apixaban	Patient characteristics

Chronically prescribed medicines

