7.1.2.1. Calculation of propensity score

Propensity scores will be estimated by calendar year of index date based on multivariable logistic regression analyses that incorporate potential predictors of therapy as independent variables in the regression and cohort status (prescription of warfarin or apixaban) as the outcome. Consecutive calendar years of index dates may be collapsed to build logistic regression model with robustness. The following covariates will be included in the logistic regression:

- age on index date
- age at NVAF diagnosis
- gender

PFIZER CONFIDENTIAL

- CHADS₂ score in baseline
- CHA₂DS₂-VASc score in baseline
- heart failure diagnosis in baseline
- coronary heart disease diagnosis in baseline
- peripheral arterial disorder diagnosis in baseline
- myocardial infarction diagnosis in baseline
- hyperthyroidism or thyrotoxicosis in baseline
- TIA diagnosis in baseline
- stroke or SE diagnosis in baseline
- renal dysfunction diagnosis in baseline
- liver dysfunction diagnosis in baseline
- bleeding diagnosis in baseline
- hypertension diagnosis in baseline
- diabetes mellitus diagnosis in baseline
- treated with antiplatelet drug in baseline
- treated with NSAIDs in baseline
- treated with gastric secretion inhibitor in baseline
- treated with statin-based drug in baseline
- treated with anti-hypertensives in baseline
- treated with anti-arrhythmics in baseline
- treated with beta-blockers in baseline
- treated with heparins in baseline
- cardioversion in baseline

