7.2.3. Sensitivity analysis

E-values will be calculated to assess the extent of unmeasured confounding on findings from primary analyses of effectiveness and safety outcomes. E-value is a measure developed by VanderWeele and Ding (2017) as the minimal strength of association between a hypothetical unmeasured confounder with both the treatment and outcome to explain away the identified association between treatment and the outcome.

PFIZER CONFIDENTIAL

Page 19 of 51

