	1259	
Myocardial infarction	1200	Exclude intermediate angina syndrome, preinfarction
	1200	syndrome, initial arbeits angina, intermediate coronary syndrome
	1210	
	l211	
	1212	
	1214	
	1240	
	1241	Exclude Dressler syndrome
Renal impairment	1120	
	1129	
	1139	
	N003	
	N009	
	N032	
	N033	
	N039	
	N040	
	N044	
	N049	
	N052	

Page 26 of 51

Variable Used	ICD-10	Additional rules
in Study	Code [*] N055	on Data Extraction
	N055	
	N059	
	N170	
	N171	
	N172	
	N178	
	N179	
	N189	
	N19	Exclude renal anemia, afunctional kidney, and alimentary proteinuria
Liver dysfunction	B150	
	B159	
	B162	
	B169	
	B171	
	B172	
	B178	
	B179	
	B181	
	B182	
	B189	
	B190	
	B199	
	C220	
	K700	
	K701	
	K703	
	K709	
	K716	
	K720	
	K721	
	K729	
	K730	
	K732	
	K738	
	K739	
	K740	

Page 27 of 51

Variable Used in Study	ICD-10 Code [*]	Additional rules on Data Extraction
	K741	
	K743	
	K744	
	K745	
	K746	
	K750	
	K751	
	K754	
	K759	
	K760	
	K761	
	K762	
	K763	
	K766	
	K767	
	K768	
	K769	
Cancer	C00	
	C01	
	C02	
	C03	
	C04	
	C05	
	C06	
	C07	
	C08	
	C09	
	C10	
	C11	
	C12	
	C13	
	C14	
	C15	
	C16	
	C17	
	C18	
	C19	

Page 28 of 51

Variable Used in Study	ICD-10 Code [*]	Additional rules on Data Extraction
	C20	
	C21	
	C22	
	C23	
	C24	
	C25	
	C26	
	C30	
	C31	
	C32	
	C33	
	C34	
	C37	
	C38	
	C40	
	C41	
	C43	
	C44	
	C45	
	C46	
	C47	
	C48	
	C49	
	C50	
	C51	
	C52	
	C53	
	C54	
	C55	
	C56	
	C57	
	C58	
	C60	
	C61	
	C62	
	C63	

Page 29 of 51

Variable Used in Study	ICD-10 Code [*]	Additional rules on Data Extraction
	C64	
	C65	
	C66	
	C67	
	C68	
	C69	
	C70	
	C71	
	C72	
	C73	
	C74	
	C75	
	C76	
	C78	
	C79	
	C80	
	C81	
	C82	
	C83	
	C84	
	C85	
	C88	
	C90	
	C91	
	C92	
	C93	
	C94	
	C95	
	C96	
	C97	
	D00	
	D01	
	D02	
	D03	
	D04	
	D05	

Page 30 of 51

Variable Used in Study	ICD-10 Code [*]	Additional rules on Data Extraction
	D06	
	D07	
	D09	
	D10	
	D11	
	D12	
	D13	
	D14	
	D15	
	D16	
	D17	
	D18	
	D19	
	D20	
	D21	
	D22	
	D23	
	D24	
	D25	
	D27	
	D28	
	D29	
	D30	
	D31	
	D32	
	D33	
	D34	
	D35	
	D36	
	D37	
	D38	
	D39	
	D40	
	D41	
	D42	
	D43	

Page 31 of 51

Variable Used in Study	ICD-10 Code [*]	Additional rules on Data Extraction
	D44	
	D45	
	D46	
	D48	

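### The SAP's renal-impairment code list takes only N189 from the N18 block, so patients coded solely with other N18 codes enter the propensity score as having no renal dysfunction

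*SAP*

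**What the plan says.** SAP 7.1.2.1 lists the covariates of the propensity model. The only renal one is "renal dysfunction diagnosis in baseline". No other code list in the appendix fits that label, so it must be built from the rows headed "Renal impairment" in SAP 10.3.1.

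Those rows end with five N17 codes, then N189, then N19. The only extraction note in the renal list is "Exclude renal anemia, afunctional kidney, and alimentary proteinuria". It is printed against N19, and N189 carries no note.

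eGFR and serum creatinine appear in SAP 5.4 as patient characteristics, in continuous and categorical form, but are not in the 7.1.2.1 list. SAP 10.3.5 has a renal-impairment row, in a table whose first column is headed as subgroups, that points back to 10.3.1.

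**The concern.** Renal function plausibly influences both the choice between warfarin and apixaban and the risk of bleeding and stroke, so it belongs among the main confounders. The weighting can balance it only as well as the flag measures it. If the flag omits most of a diagnostic block, patients with recorded kidney disease are weighted as though they had none. Any difference between cohorts in how common such patients are then stays in the hazard ratios for both primary endpoints.

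A final digit of 9 adds to the doubt. In the SAP's own labels in 10.3.4 it often marks the unspecified category (for example I609, N309 and N939). By that pattern the list would keep the residual N18 code and drop the specified ones.

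**Working it through.** The plan gives no figure on this point, so the check is of the code list, followed by an illustration of scale.

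**1. The list.** Reading an initial 1 as the letter I where the PDF conversion changed it, the distinct renal codes are: I120, I129, I139; N003, N009, N032, N033, N039, N040, N044, N049, N052, N055, N059; N170, N171, N172, N178, N179; N189; N19. That is 3 + 11 + 5 + 1 + 1 = 21 codes. Exactly one begins with N18. The rows from N170 to N19 read in clean order, so conversion damage does not explain the gap.

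**2. Is N189 shorthand for the block?** The SAP enters whole blocks as three characters: N19 in the next row, E10 to E14 for diabetes, K25 to K28 for peptic ulcer. The neighbouring N17 block is entered code by code. On either convention N189 stands for itself alone.

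**3. Who is missed?** A patient is scored as without renal dysfunction only if every renal code in the baseline period is unlisted. A patient with another N18 code who also has N189, N19, I120, I129, I139, a listed glomerular code or an N17 code is still flagged.

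**4. Does another part of the plan recover them?**
- Propensity model: 26 covariates, one renal term, no laboratory value.
- Balance check (SAP 7.1.2.2): covers baseline variables, so it could show a difference in eGFR or creatinine where these are recorded. Missing values are not imputed (SAP 6).
- Cox adjustment (SAP 7.1.2.5): triggered by imbalance in variables that are in the propensity score. An imbalance in eGFR or creatinine does not trigger it.
- Sensitivity analysis (SAP 7.2.3): E-values only, with no alternative renal definition.

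**5. Edition.** The available text names no ICD-10 edition. The same conditions carry different codes in two lists: haemorrhoids under I84 and pancreatitis as K85 in 10.3.4, but K649 and K859 in 10.3.5. That is the pattern that mixed editions would leave. Index dates run from 2013 to 2021.

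**6. Scale, all inputs assumed.** Let pW and pA be the prevalence of missed renal disease in the warfarin and apixaban cohorts, and RR its rate ratio for the outcome. The hazard ratio is multiplied by about (1 + pA(RR − 1)) / (1 + pW(RR − 1)).

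| pW | pA | RR | Calculation | Factor |
|---|---|---|---|---|
| 4% | 2% | 1.5 | 1.01/1.02 | 0.990 |
| 8% | 3% | 2 | 1.03/1.08 | 0.954 |
| 10% | 4% | 3 | 1.08/1.20 | 0.900 |
| 15% | 5% | 3 | 1.10/1.30 | 0.846 |
| 5% | 5% | 3 | 1.10/1.10 | 1.000 |
| 4% | 10% | 3 | 1.20/1.08 | 1.111 |

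To see what this means, suppose that the study observed its planning hazard ratios (SAP 4.5). Removing a factor of 0.900 gives 0.59/0.900 = 0.66 for major bleeding and 0.53/0.900 = 0.59 for stroke/SE. Removing 0.846 gives 0.70 and 0.63. These figures make no allowance for covariates in the score that correlate with renal disease, such as heart failure, hypertension and diabetes.

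**The case against.** The strongest reply is that the gap may be empty. The documents do not say how this database codes chronic kidney disease, and many rows of the appendix select disease names within a code, so local mapping matters. If nearly all such patients carry N189 or another listed code, nothing changes. Exclusion 7 also removes "or patients treated with OAC but in 'off-label' or 'contraindicated' manners", which may take out some severe renal cases, though no renal threshold is given. E-values are planned too: "E-values will be calculated to assess the extent of unmeasured confounding on findings from primary analyses of effectiveness and safety outcomes". All this stands as a limit on size. It does not justify the list, because no reason for leaving out the other codes is given. An E-value describes how strong a confounder would have to be; it does not correct a flag that can be corrected.

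A reader might infer four stronger things, and the documents support none of them:
- *All staged and end-stage kidney disease counts as no renal dysfunction.* Step 3 shows that this depends on having no other listed code. The meaning of the individual N18 codes comes from the classification, not from the SAP.
- *The balance check is blind to the problem.* It could show imbalance in eGFR or creatinine where recorded. The restriction lies in the Cox adjustment rule.
- *A renal subgroup comparison is contaminated.* Every visible row of SAP 7.2.4 gives the subgroup as none, and text that might define such a group is redacted.
- *Apixaban is made to look better by a known amount.* Both size and direction depend on assumed prevalences.

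**Conclusion.** The point holds in a limited form. Followed as written, the list gives an incomplete measure of a key confounder, and neither the weighting nor the Cox adjustment rule corrects for it. The affected patients are those whose only baseline renal codes are N18 codes other than N189. Their number is unknown and could be close to zero or material.

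If missed disease is commoner on warfarin, the assumed inputs shift the hazard ratio by about 1% to 15% in favour of apixaban. If it is equally common in both cohorts there is no such bias. If it is commoner on apixaban the shift goes the other way. The conclusion rests on the printed list being the one programmed, and on N18 being the chronic kidney disease block of the classification that the SAP uses. The change is worth making because it is concrete and cheap, not because a large bias has been shown.

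**What to change.** - In SAP 10.3.1, replace N189 with the whole N18 block, and state which ICD-10 edition or editions apply to records over 2013 to 2021.
- Re-derive the renal covariate and the stabilised weights, and any group that reaches 10.3.1 through 10.3.5.
- Report the number of patients reclassified, by cohort and index year. Index year matters because the propensity scores are estimated by calendar year and coding may have changed over the period. A small count in both cohorts would settle the matter.

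The cost is one row of the code list and a rerun of the propensity model and the analyses that use its weights. No new data should be needed, provided that the extract holds the patients' full diagnosis records.

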10.3.2. List of procedure code

Procedure	Procedure Code
Cardiac surgery	150138210
	150138310
	150138410
	150138510
	150359210
	150138710
	150140510
	150140610
	150140710
	150139010
	150140810
	150318010
	150317810
	150318110
	150331450
	150331550
	150331950
	150332050
	150317910
	150318210
	150140010
	150139210
	150153910
	150374910
	150375010
	150375110
	150260350
	150284310
	150359310
	150263310

PFIZER CONFIDENTIAL

Procedure	Procedure Code
	150375210
	150375310
	150375410
	160107550
	150139810
	150139910
	150318310
	150145710
	150145810
	150145910
	150146010
	150318410
	150318510
	150302770
	150143010
	150143110
	150331650
	150332150
	150318710
	150319010
	150319310
	150318810
	150319110
	150319410
	150328750
	150328850
	150331750
	150331850
	150332250
	150332350
	150318910
	150319210
	150319510
	150318610
	150141010
	150279510
	150279610
	150141410

Page 33 of 51

Procedure	Procedure Code
	150141610
	150369950
	150141710
	150359470
	150143610
	150260050
	150143710
	150143810
	150141510
	150375570
	150375670
	150375770
	150319610
	150292910
	150139310
	150140910
	150242550
	150244910
	150245010
	150359510
	150359610
	150381150
	150381250
	150381350
	150381450
	150150010
	150381550
	150275910
	150359710
	150359810
	150359910
	150381650
	150381750
	150381850
	150381950
	150150110
	150382050
	150245110

Page 34 of 51

Procedure	Procedure Code
	150245210
	150375870
	150375970
	150376070
	150141210
	150301310
	150267850
	150319710
	150151810
	150376110
	150139110
	150319810
	150138810
	150151910
	150320010
	150346410
	150320110
	150147150
	150144110
	150320210
	150320310
	150142710
	150139410
	150320410
	150142910
	150320510
	150260150
	150346510
	150145110
	150145010
	150376210
	150376310
	150143250
	150143350
	150143450
	150143550
	150283250
	150283350

Page 35 of 51

Procedure	Procedure Code
	150283450
	150283550
	150144910
	150139610
	150142410
	150141810
	150141910
	150320610
	150142050
	150142110
	150142210
	150142310
	150142810
	150144010
	150320710
	150144210
	150144550
	150147410
	150147510
	150320810
	150320910
	150144410
	150144650
	150144750
	150146510
	150146610
	150321010
	150321110
	150321210
	150376470
	150146910
	150146810
	150321310
	150142510
	150329810
	150145310
	150329910
	150139510

Page 36 of 51
Procedure	Procedure Code
	150330010
	150147010
	150330110
	150376570
	150321410
	150321510
	150376670
	150147310
	150145650
	150141310
	150321810
	150321610
	150321910
	150146710
	150321710
	150330210
	150330310
	150376770
	150293010
	150330410
	150145510
	150302870
	150145410
	150322010
	150322110
	150144310
	150147250
	150346610
	150144810
	150253810
	150253910
	150275610
	150346710
	150262810
	150303310
	150267310
	150140110
	150140210

Page 37 of 51

Procedure	Procedure Code
	150140410
	150346910
	150347010
	150303210
	150322210
	150275210
	150275310
	150336910
	150337010
	150360010
	150148010
	150148110
	150147610
	150147910
	150147770
	150147870
	150347170
	150275870
	150262910
	150275710
	150266110
	150382650
	150266210
	150382750
	150301810
	150382850
	150303410
	150303510
	150360110
	150360210
	150360310
	150360410
	150303610
	150303710
	150322410
	150322610
Ablation	150346710
	150262810

Procedure	Procedure Code
	150303310
	150346870
	150370050
Electrical defibrillation	140051410
	140010310
	140055010
	150275210
	150275310
	150336910
	150337010
	150370550
Heart valve prosthesis implantation surgery	150141410
	150141610
	150141710
	150359470
	150369950
	150331950
	150332050
	150332150
	150328850
	150332250
	150332350
	150141510
	150375570
	150375670
	150375770
	150244910
	150359510
	150381150
	150381250
	150359710
	150359810
	150381650
	150381750
	150283450

Page 39 of 51

10.3.3. Stroke related medical history

Disease	ICD10 code	Standard disease code	Note
Homorrhago	160		
Hemorrhage stroke	l61		
SUDKE	162		Exclude non-traumatic extradural haemorrhage
	163		
		3489032	
		4371003	
		4379014	
Ischemic stroke		3448002	
		3448028	
		3489029	
		3489035	
		4379006	
	H340		
	G450		
TIA	G451		
	G458		
	G459		
	1740		Include only abdominal aortic embolism
	1741		Include only aortic embolism
	1742		Include only acute arterial occlusive disease of
	1/42		arteries of upper extremities
	1743		Include only femoral arterial occlusion and acute
Systemic			arterial occlusive disease of arteries of lower
embolism			extremities
	1744		
	1745		Include only iliac artery embolism
	1748		Include only hepatic artery embolism
	1749		Include only thromboembolism, embolic infarction, aortic embolism
	1748		Include only subclavian artery stenosis

10.3.4. bleeding

Procedure for definition of "bleeding"

Step 1. To extract the following group A or group B from MDV data base.

Group A: ICD-10 name includes "出血 (bleeding)" or "血腫 (ecchymoma)"

Group B: Disease name includes "出血 (bleeding)" or "血腫 (ecchymoma)"

Step 2. To select disease names considered to be relevant to side effect of OAC individually from disease names excluded in Step 1.

Step 3. To exclude disease names which are not considered to be relevant to side effect of OAC from the disease names included in Step 1.

ICD-10	ICD10Name
A162	Tuberculosis of lung, without mention of bacteriological or histological confirmation
A165	Tuberculous pleurisy, without mention of bacteriological or histological confirmation

ICD-10	ICD10Name				
B303	Acute epidemic haemorrhagic conjunctivitis (enteroviral)				
D500	Iron deficiency anaemia secondary to blood loss (chronic)				
D62	Acute posthaemorrhagic anaemia				
D66	Hereditary factor VIII deficiency				
D683	Haemorrhagic disorder due to circulating anticoagulants				
D698	Other specified haemorrhagic conditions				
D699	Haemorrhagic condition, unspecified				
E078	Other specified disorders of thyroid				
E274	Other and unspecified adrenocortical insufficiency				
G361	Acute and subacute haemorrhagic leukoencephalitis [Hurst]				
G951	Vascular myelopathies				
G968	Other specified disorders of central nervous system				
H052	Exophthalmic conditions				
H113	Conjunctival haemorrhage				
H168	Other keratitis				
H208	Other iridocyclitis				
H210	Hyphaema				
H313	Choroidal haemorrhage and rupture				
H350	Background retinopathy and retinal vascular changes				
H356	Retinal haemorrhage				
H357	Separation of retinal layers				
H405	Glaucoma secondary to other eye disorders				
H431	Vitreous haemorrhage				
H448	Other disorders of globe				
H470	Disorders of optic nerve, not elsewhere classified				
H603	Other infective otitis externa				
H669	Otitis media, unspecified				
H738	Other specified disorders of tympanic membrane				
H922	Otorrhagia				
1213	Acute transmural myocardial infarction of unspecified site				
1230	Haemopericardium as current complication following acute myocardial infarction				
1312	Haemopericardium, not elsewhere classified				
1600	Subarachnoid haemorrhage from carotid siphon and bifurcation				
1601	Subarachnoid haemorrhage from middle cerebral artery				
1602	Subarachnoid haemorrhage from anterior communicating artery				
1603	Subarachnoid haemorrhage from posterior communicating artery				
1604	Subarachnoid haemorrhage from basilar artery				
1605	Subarachnoid haemorrhage from vertebral artery				
1606	Subarachnoid haemorrhage from other intracranial arteries				
1607	Subarachnoid haemorrhage from intracranial artery, unspecified				
1608	Other subarachnoid haemorrhage				
1609	Subarachnoid haemorrhage, unspecified				

ICD-10	ICD10Name				
l610	Intracerebral haemorrhage in hemisphere, subcortical				
l611	Intracerebral haemorrhage in hemisphere, cortical				
l613	Intracerebral haemorrhage in brain stem				
l614	Intracerebral haemorrhage in cerebellum				
1615	Intracerebral haemorrhage, intraventricular				
l616	Intracerebral haemorrhage, multiple localized				
l618	Other intracerebral haemorrhage				
1619	Intracerebral haemorrhage, unspecified				
1620	Subdural haemorrhage (acute)(nontraumatic)				
l621	Nontraumatic extradural haemorrhage				
1629	Intracranial haemorrhage (nontraumatic), unspecified				
1638	Other cerebral infarction				
1690	Sequelae of subarachnoid haemorrhage				
1691	Sequelae of intracerebral haemorrhage				
1780	Hereditary haemorrhagic telangiectasia				
1788	Other diseases of capillaries				
1841	Internal hemorrhoid with other complications				
1844	External hemorrhoid with other complications				
1848	Unspecified hemorrhoid with other complications				
1850	Oesophageal varices with bleeding				
1864	Gastric varices				
J041	Acute tracheitis				
J339	Nasal polyp, unspecified				
J90	Pleural effusion, not elsewhere classified				
J942	Haemothorax				
J950	Tracheostomy malfunction				
